Subjects in both cohorts will reduce the dose by one capsule per week, as necessary, and no more frequently than at biweekly intervals, in the event that any one of the following four criteria are met: plasma iPTH is confirmed to be <35 pg/mL (for subjects with stage 3 CKD) or <70 pg/mL (for subjects with stage 4 CKD), serum calcium (corrected) is confirmed to be >10.3 mg/dL, serum total 25-hydroxyvitamin D is confirmed to be >100 ng/mL, or serum phosphorus is confirmed to be >5.5 mg/dL (ages 12 to <18 years) or >6.0 mg/dL (ages 8 to <12 years), provided that the investigator has deemed the elevated serum phosphorus to be related to study drug administration and has taken appropriate and persistent actions to control serum phosphorus by initiating or adjusting any phosphate binder therapy.

Dose reductions will be accomplished by consistently omitting doses on a specific day of the week, as follows:

- First dose reduction: Dosing will be omitted on all Mondays (M).
- Second dose reduction: Dosing will be omitted on all M and Wednesdays (W)
- Third dose reduction: Dosing will be omitted on all M, W and Fridays (F)
- Fourth dose reduction: Dosing will be omitted on all M, W, F and Sundays (S)

Any subject who requires a further dose reduction will terminate dosing with study drugs and immediately commence the 6-week FU period.

Subjects on dose reduction will be allowed an unscheduled safety visit if deemed appropriate by the investigator to have FU blood sampling within 48 hours of any dose reduction.

A summary of the initial and reduced weekly dose levels, in mcg units, after each of the four possible dose reductions appears in the table below:

Daily (mcg)	Weekly (mcg)	Weekly Dose (mcg)			
		1 st Reduction	2 nd Reduction	3 rd Reduction	4 th Reduction
60	420	360	300	240	180
30	210	180	150	120	90
0	0	0	0	0	0

Subjects will suspend dosing if plasma iPTH is persistently <30 pg/mL (three consecutive visits) or serum calcium (corrected) is confirmed to be >11.0 mg/dL, and resume when iPTH is ≥ 35 pg/mL and serum calcium is <9.8 mg/dL at the next lower dose level.

Primary Efficacy Endpoint:

The primary estimand is the reduction of mean plasma iPTH by at least 30% from pre-treatment baseline. The primary efficacy endpoint is the proportion of subjects in the intent-to-treat (ITT) population (age 8 to <18 years) attaining a mean decrease in plasma iPTH of at least 30% from pre-treatment baseline compared to placebo during the EAP.

Primary Safety Endpoints:

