5.4 Dose Reduction Criteria

Subjects will reduce the dose through the IRS by one capsule per week, as necessary, and no more frequently than at biweekly intervals, in the event that any one of the following four criteria are met:

1. Two consecutive visits with plasma iPTH <35 pg/mL (for subjects with stage 3 CKD) or <70 pg/mL (for subjects with stage 4 CKD),
2. Two consecutive visits with serum calcium (corrected) >10.3 mg/dL,
3. Two consecutive visits with serum total 25-hydroxyvitamin D >100 ng/mL, or
4. Two consecutive visits with serum phosphorus >5.5 mg/dL (ages 12 to <18 years), or >6.0 mg/dL (ages 8 to <12 years) provided that the investigator has deemed the elevated serum phosphorus to be related to study drug administration and has taken appropriate and persistent actions to control serum phosphorus by initiating or adjusting any phosphate binder therapy.

Dose reductions will be accomplished by consistently omitting doses on a specific day of the week, as follows:

- First dose reduction: Dosing will be omitted on all M.
- Second dose reduction: Dosing will be omitted on all M and W
- Third dose reduction: Dosing will be omitted on all M, W and F

- Fourth dose reduction: Dosing will be omitted on all M, W, F and S

Any subject who requires a further dose reduction will terminate dosing with study drugs and commence the 6-week FU period.

Subjects on dose reduction will be allowed a safety visit if deemed appropriate by the investigator to have FU blood sampling within 48 hours of dose reduction.

A summary of the initial and reduced weekly dose levels, in mcg units, after each of the four possible dose reductions appears in the table below:

Daily (mcg)	Weekly					Dose (mcg)
	Weekly (mcg)	1 st Reduction	2 nd Reduction	3 rd Reduction	4 th Reduction	
60	420	360	300	240	180	
30	210	180	150	120	90	
0	0	0	0	0	0	

Subjects will suspend dosing if plasma iPTH is persistently <30 pg/mL (three consecutive visits) or serum calcium (corrected) is confirmed to be >11.0 mg/dL, and resume when iPTH is \geq 35 pg/mL (for subjects with stage 3 CKD) or \geq 70 pg/mL (for subjects with stage 4 CKD) and serum calcium is \leq 9.8 mg/dL at the next lower dose level.

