5.6 Method of Assigning Subjects to Treatment Groups

After signing the ICF, prior to any study-related activities, subjects will be assigned a site-generated, ascending subject identification number and will retain that number throughout the study. Should a subject be withdrawn from the study, the subject identification number will not be reassigned. Approximately 350 subjects will be screened to enroll approximately 108 subjects who meet the enrollment criteria.

An IRS will provide study treatment group assignments for these 108 subjects using the computer-generated randomization code provided by the IRS vendor. The randomization code will be stratified age group (8 to <12 years and 12 to <18 years) and balanced within each age group for gender and CKD stage (stages 3 and 4).

In Cohort 1 (ages 12 to <18 years), approximately 72 subjects, balanced for gender and CKD stage, will be randomized in a 2:1 ratio to active or placebo treatment, respectively. Ten (10) subjects will be randomly selected from the active group and five (5) subjects will be randomly selected from the placebo group for intensive PK evaluation during the last 3 days of the 12th week of treatment (prior to dose escalation). Twenty other subjects will be randomly selected for end of study PK evaluations from the active group, ten of which will be receiving an end of study dose of 30 mcg/day and the other ten will receiving an end of study dose of 60 mcg/day.

In Cohort 2 (ages 8 to <12 years), approximately 36 subjects, balanced for gender and CKD stage, will be randomized in a 2:1 ratio to active or placebo treatment, respectively. Ten (10) subjects will be randomly selected from the active group and five (5) subjects will be randomly selected from the placebo group for intensive PK evaluation during the last 3 days of the 12th week of treatment (prior to dose escalation). End of study PK evaluations will be made after 26 weeks of treatment. Twenty other subjects will be randomly selected for end of study PK evaluations from the active group, ten of which will be receiving an end of study dose of 30 mcg/day and the other ten will receiving an end of study dose of 60 mcg/day.

For both cohorts, an IRS will provide study treatment group assignments using the computer-generated randomization code.

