7.2 Treatment Period (Weeks 1-26)

7.2.1 Visits 4-10 (Days 8-71)

- May occur ± 3 days of scheduled day
- AE assessment
- Concomitant medications

- VS measurements
- Blood samples drawn for:
 - Chemistry (partial panel)
 - Plasma iPTH
 - Serum total 25-hydroxyvitamin D

7.2.2 *Visits 11-12 (Days 83-84)*

- Must occur on the scheduled days
- AE Assessment
- Concomitant medications
- VS measurements
- Blood samples drawn for all subjects at 0 (pre-dose), 6 and 12 hours and additionally, only for subjects assigned to intensive PK evaluation, at -2, 2, 4 and 8 hours after dosing on Day 83 for:
 - Chemistry (partial panel)
 - Serum 25-hydroxyvitamin D₃, [REDACTED]
- Blood samples drawn at 24 hours ±4 hours before dosing on Day 84 for:
 - Chemistry (partial panel)
 - Serum 25-hydroxyvitamin D₃, [REDACTED]

7.2.3 *Visit 13 (Day 85):*

- Must occur on the scheduled day
- Urine pregnancy (for females of childbearing potential)
- AE assessment
- Concomitant medications
- Urine pregnancy (only for females of childbearing potential)
- VS measurement
- Urine chemistry and urinalysis
- Blood samples drawn at 48 hours ±4 hours before dosing for:
 - Chemistry (full panel) and hematology
 - Plasma iPTH
 - Serum total 25-hydroxyvitamin D
 - Serum 25-hydroxyvitamin D₃, [REDACTED]
 - [REDACTED]
- Drug accountability
- Patient reported palatability and acceptability

- Dispense assigned bottles of study drug

7.2.4 *Visits 14-21 (Days 92-169)*

- May occur ± 3 days of scheduled day
- Visits 14 and 16 are required only for subjects who underwent upward dose titration at visit 13
- AE assessment
- Concomitant medications
- VS measurements
- Blood samples drawn for:
 - Chemistry (partial panel)
 - Plasma iPTH
 - Serum total 25-hydroxyvitamin D

7.2.5 *Visit 22 (Day 183):*

- Must occur on the scheduled day
- Urine pregnancy (only for females of childbearing potential)
- AE assessment
- Concomitant medications
- VS measurements
- Urine chemistry and urinalysis
- Blood samples drawn for:
 - Chemistry (full panel) and hematology
 - Plasma iPTH
 - Serum total 25-hydroxyvitamin D
 - Serum 25-hydroxyvitamin D₃, [REDACTED]
 - [REDACTED]
- Patient reported palatability and acceptability
- Drug accountability

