7.3 Follow-up Period or Second PK Assessment

7.3.1 *Visit 23 (Day 190)*

- Must occur on the scheduled day
- Required only for subjects participating in the second PK assessment
- AE Assessment

- Concomitant medications
- VS measurements
- Blood samples drawn for:
 - Chemistry (partial panel)
 - Serum 25-hydroxyvitamin D₃, [REDACTED]

7.3.2 *Visit 24 (Day 197)*

- May occur ± 3 day of scheduled day
- Required only for subjects participating in the second PK assessment
- Concomitant medications
- AE assessment
- VS measurements
- Blood samples drawn for:
 - Chemistry (full panel) and hematology
 - Plasma iPTH
 - Serum total 25-hydroxyvitamin D
 - Serum 25-hydroxyvitamin D₃, [REDACTED]

7.3.3 *Visits 25-27 (Days 204-218)*

- Must occur on the scheduled days
- Required only for subjects participating in the second PK assessment
- AE Assessment
- Concomitant medications
- VS measurements
- Blood samples drawn for:
 - Chemistry (partial panel)
 - Serum 25-hydroxyvitamin D₃, [REDACTED]

7.3.4 *Visit 28/ET (Day 225)*

- May occur ± 3 day of scheduled day
- Concomitant medications
- AE assessment
- PE (including weight, height and BMI)
- VS measurements
- 12-lead ECG

- Urine chemistry and urinalysis
- Urine pregnancy (only for females of childbearing potential)
- Blood samples drawn for:
 - Chemistry (full panel) and hematology
 - Plasma iPTH
 - Serum total 25-hydroxyvitamin D
 - Serum 25-hydroxyvitamin D₃, [REDACTED]
 - [REDACTED]

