All ECG values will be listed.

9.11.2 *Secondary Endpoint Analyses*

The number (n, %) of subjects with hypercalciuria (>200 mg Ca/g creatinine), hypercalcemia (two consecutive visits with serum calcium >10.3 mg/dL) or hyperphosphatemia (two consecutive visits with serum phosphorus >5.5 mg/dL deemed to be study drug related) or serum confirmed CaxP product >55 (for Cohort 1) or >60 (for Cohort 2) will be compared between the treatment groups (active versus placebo) using the Cochran-Mantel-Haenszel test statistic (alpha=0.05) for overall efficacy of the multicenter results; the Chi-square test or Fisher's Exact test will be used for reporting the results in the separate strata.

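### The calcium, phosphorus and CaxP safety comparison counts two-visit events over visit schedules that differ by arm, which modestly inflates the active-arm count

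*Combined protocol and SAP*

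**What the plan says.** Section 9.11.2 compares the arms by Cochran-Mantel-Haenszel test at alpha 0.05 on three events relevant here:

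- "hypercalcemia (two consecutive visits with serum calcium >10.3 mg/dL";
- hyperphosphatemia, "two consecutive visits with serum phosphorus >5.5 mg/dL deemed to be study drug related";
- "serum confirmed CaxP product >55 (for Cohort 1) or >60 (for Cohort 2".

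The Synopsis plans the same comparison in terms of confirmed values. Neither place names an analysis window or a visit set.

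The visit schedule depends on the arm:

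- Section 7.2.4: "Visits 14 and 16 are required only for subjects who underwent upward dose titration at visit 13". Section 5.3 titrates only subjects on active treatment, and no sham titration is described.
- Section 7.3, for each of Visits 23 to 27: "Required only for subjects participating in the second PK assessment". Section 5.6 sets that subset for each cohort: "Twenty other subjects will be randomly selected for end of study PK evaluations from the active group".
- All seven visits draw a chemistry panel (Sections 7.2.4 and 7.3). Even the partial panel in Table 2 includes calcium, phosphorus and albumin.

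**The concern.** The chance that a subject ever has two adjacent values above a threshold rises with the number of visits and with how close together they are. If one arm is looked at more often, its event proportion rises even when the drug does nothing.

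The meaning of *consecutive* also shifts. After Visit 22 (Day 183), a second-PK subject is next measured on Day 190. A placebo subject is next measured on Day 225, 42 days after Visit 22.

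The incidence of hypercalcemia and hyperphosphatemia against placebo is a stated secondary objective (Section 2.1.2). With 72 and 36 subjects and probably few events, one or two schedule-driven cases could suggest a pediatric safety signal that is not there. They could equally give grounds to dismiss a real signal as an artefact of the schedule.

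**Working it through.** The plan gives no event rate or power for these endpoints, so it has no figure of its own to reproduce.

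**1. Visit counts (Sections 7.2 and 7.3, Appendix 1).** Common to everyone: Visits 4-13 (10), 15 (1), 17-22 (6) and 28 (1), which is 18 visits and 17 adjacent pairs.

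- Titrated only: 18 + 2 = 20.
- Second PK subset only: 18 + 5 = 23.
- Both: 18 + 7 = 25 visits, 24 pairs.

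**2. How many active subjects can be in the second PK subset.** The plan says 20 per cohort, chosen from active subjects other than the 10 in intensive PK. Cohort 1 has 72 × 2/3 = 48 active; 48 − 10 = 38, so 20 is possible. Cohort 2 has 36 × 2/3 = 24 active; 24 − 10 = 14, so 20 is not. The ceiling is 20 + 14 = 34, before dropout. At least 72 − 34 = 38 active subjects have the same 42-day gap as placebo.

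**3. Equal risk, independent visits.** Let p be the chance that one visit is above threshold (assumed) and q(n) the chance of no two adjacent high visits among n. Then q(n) = (1−p)·q(n−1) + p(1−p)·q(n−2), with q(0) = q(1) = 1, and the event probability is 1 − q(n).

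| p | 18 visits | 20 | 23 | 25 | ratio 25:18 |
|---|---|---|---|---|---|
| 0.01 | 0.0017 | 0.0019 | 0.0022 | 0.0024 | 1.41 |
| 0.05 | 0.0399 | 0.0445 | 0.0513 | 0.0558 | 1.40 |
| 0.10 | 0.1456 | 0.1612 | 0.1840 | 0.1989 | 1.37 |

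**4. Averaged over the active arm.** As an illustration, assume 36 titrated and 34 in the PK subset, 17 of them in both. That leaves 19 with neither, 19 titrated only, 17 PK only and 17 both. At p = 0.05:

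(19 × 0.0399 + 19 × 0.0445 + 17 × 0.0513 + 17 × 0.0558)/72 = 0.0476.

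The ratio is 0.0476/0.0399 = 1.19, or 72 × (0.0476 − 0.0399) ≈ 0.55 extra subjects. At p = 0.10 the ratio is 1.18 with 1.9 extra subjects. At p = 0.01 it is 1.20 with 0.02 extra.

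**5. Correlated values.** A simulation gave both arms the same risk. It assumed p of 0.01 to 0.10, correlation times of 3 to 28 days, and a between-subject variance share of 0 or 0.5. The days of Visits 15-18 were inferred, because the Appendix 1 header is broken in the text. Whole-arm ratios were:

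- 1.06-1.24 with 36 titrated and 20 in the PK subset;
- 1.09-1.33 with 36 and 34;
- 1.10-1.39 with 58 and 34.

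An extra normal value can break a run, but the net effect was upward in every scenario. At p of 0.05 to 0.10, the rate of falsely finding active higher was 0.022-0.096, against 0.009-0.024 when both arms had the common 18 visits. At p of 0.01 to 0.02 it stayed at or below 0.023.

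**6. Applying the titration rule.** Section 5.3 titrates only subjects whose week-12 calcium and phosphorus are within limits, so those who receive Visits 14 and 16 are selected for lower values. The rerun assumed:

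- calcium mean 9.4-9.5 mg/dL and phosphorus mean 4.4-4.6 mg/dL;
- 50-80% of eligible subjects titrated;
- a PK subset of 20-34, half of them titrated.

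The whole-arm ratio was 1.06-1.20. From a 3.7% calcium event rate, the excess was 0.3-0.5 subjects in 72. From a 7.5% phosphorus rate, before any relatedness judgement, it was 0.6-1.0. The highest-rate scenarios reached 1.4 and 2.0. A further run with the PK subset at 34 gave 1.10-1.16, or about 0.4-1.5 extra subjects.

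**7. Common visits only.** Both arms have 18 visits, the equal-risk ratio is 1.0, and the simulated two-sided type I error was at most 0.049.

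**The case against.** The strongest reply is that the effect is small and works against the sponsor. Only subjects both titrated and in the PK subset get all seven extra visits. A reader might carry the 1.4 ratio for such a subject over to the tested comparison, or assume the nominal 40 PK subjects, but Section 5.6 does not allow 40 and the test compares whole arms. If events are rare, the test stays conservative. All of this stands and limits the size.

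Two points about scope also stand. Hyperphosphatemia requires a judgement of drug relatedness, so raw phosphorus exceedances overstate that endpoint. For CaxP, the text says confirmed rather than two visits. Reading these as the same is an inference: the Synopsis dose-reduction text says "serum calcium (corrected) is confirmed to be >10.3 mg/dL" where Section 5.4 says "Two consecutive visits with serum calcium (corrected) >10.3 mg/dL".

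One might also answer that five of the seven visits fall after treatment and would be excluded. Section 9.11.2 does not say so. Borrowing the 30-day window of Section 6.6.9 would make the follow-up imbalance worse: Day 183 + 30 = Day 213 keeps Visits 23-26 (Days 190-211) and drops Day 225, the only placebo follow-up visit. A treatment-period window would still leave Visits 14 and 16.

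Finally, restricting the test to common visits drops the visits just after the dose increase. An excursion confirmed there can lead to a dose reduction under Section 5.4, after which values may fall and the event may not appear in the common list. This stands, and it is why the restricted analysis should not replace the all-visit one.

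**Conclusion.** The point holds. The unequal ascertainment follows from the documents; its size rests on assumed exceedance rates, correlations and titration fractions. A whole-arm ratio of about 1.1 to 1.2 is typical (1.06 to 1.39 across the scenarios run), or roughly 0.3 to 2 extra subjects of 72, and close to none if excursions are very rare. The bias makes the drug look worse.

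Three stronger readings are not supported:

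- That every active subject gets seven extra chances: they get 0, 2, 5 or 7.
- That this is the trial's only inferential test of these proportions: Section 9.11.2 adds chi-square or Fisher tests by stratum, and Section 9.11.1.2 mentions a z-test or t-test for proportions.
- That the intensive PK subset adds to the imbalance: Section 5.6 draws it 10 to 5, in line with the 2:1 allocation.

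The hypercalciuria endpoint is not affected.

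**What to change.** In Section 9.11.2 and the Synopsis secondary safety analysis, before unblinding:

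1. Prespecify a between-arm comparison using only the visits scheduled for every subject: Visits 4-13, 15, 17-22 and 28. *Consecutive* means adjacent in that list.
2. Report the all-visit comparison beside it.
3. Tabulate excursions at Visits 14, 16, 23-27 and unscheduled visits, so that a signal after the dose increase is not lost.
4. State whether confirmed CaxP means two consecutive visits.

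The cost is some wording, one extra analysis and one table. The common-visit version may miss some early post-titration events, which the all-visit result and the table would show.

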9.12 Other Analysis

Descriptive statistics will be applied to evaluate patient reported palatability and acceptability. In addition, the proportion of subjects attaining the mean decrease from baseline in plasma iPTH of $\geq 30\%$ in the subgroup of subjects with and without nutritional intake within 60 minutes of medication administration will be evaluated using the analysis methods described above.

10 ADMINISTRATIVE CONSIDERATIONS

10.1 Investigators and Study Administrative Structure

Investigators will be chosen based on their experience in treating SHPT in pediatric patients with stage 3 or 4 CKD with vitamin D therapies, their past successful and compliant conduct of clinical trials and their track records for subject recruitment, subject retention and high rates of data capture.

At screening, investigators will offer subjects notification of their primary care physician or nephrologist that he/she is participating in a clinical study. If the subject accepts, a brief letter outlining the study and identifying the study drug should be sent once the subject is enrolled.

10.2 Institutional Review Board Approval

GCP requires that the clinical protocol, any protocol amendments, the IB, the informed consent, and all other forms of subject information related to the study and any other necessary documents be reviewed by an IRB.

10.3 Ethical Conduct of the Study

In accordance with applicable country-specific regulations, the sponsor will obtain approval from the appropriate regulatory authority(ies) prior to initiating the study in that country.

10.4 Subject Information and Consent

The investigator or his/her qualified designee will explain the nature of the study to the subject and legal guardian, answer all questions regarding this study, and emphasize that missing data and premature termination of study participation will diminish the scientific value of the data obtained, prior to obtaining informed consent.

The investigator or his/her qualified designee will obtain informed consent from each subject or legal representative enrolled in the study, in accordance with the Declaration of Helsinki, the current version of the ICH guidelines and the local laws and applicable regulatory requirements.

It is the responsibility of the investigator to assure that the subject and legal guardian has signed the informed consent before any activity or treatment is undertaken which is not part of routine care. The subject will receive a signed copy of the ICF and the original will be retained in the site study records. The investigator or his/her designee will ensure documentation of the consent discussion in the subject's medical record/source documents. The decision by the subject and legal guardian to participate in the study is entirely voluntary. The investigator or designate must emphasize to the subject and legal guardian that consent regarding study participation may be withdrawn at any time without penalty or loss of benefits to which the subject is otherwise entitled.

If the ICF is amended during the study, the investigator must follow all applicable regulatory requirements pertaining to approval of the amended ICF by the IRB and use of the amended form (including for ongoing subjects).

10.5 Subject Confidentiality

Subject confidentiality will be strictly held in trust by the participating investigators, their staff, sponsor and their authorized representatives. This confidentiality is extended to cover testing of biological samples in addition to the clinical information relating to participating subjects.

The study protocol, documentation, data, and all other information generated will be held in strict confidence. No information concerning the study or the data will be released to any unauthorized third party, without prior written approval of the sponsor.

Authorized representatives of the sponsor, the designated contract research organization (if applicable), the study monitor, employees of government authorities such as the US FDA or other government authorities, and members of the IRB may inspect all documents and records required to be maintained by the investigator, including but not limited to, medical records (office, clinic, or hospital) and pharmacy records for the subjects in this study. The clinical study site will permit access to such records.

No information that would permit the identification of a specific individual will be provided for entry into the study database or study report. Study documentation submitted to the sponsor will identify study participants by study code and initials. The investigator will keep a separate confidential enrollment log that matches identifying study codes with the subjects' names and residencies.

